4.1.2 Definitions

4.1.2.1 Baseline Value

For S-K, Correction Phase (CP) baseline value will be established by the mean of 2 different S-K values, recorded 60 minutes apart (to confirm qualification for study entry) on the Correction Phase (CP) Day 1. Maintenance Phase (MP) baseline value will be defined as the measurement taken in the morning of the day of entering maintenance phase (Visit 6, MP Day 1). Note that two types of baseline (CP baseline and MP baseline) are defined only for S-K.

For the other variables (excluding S-K), baseline value of a parameter (eg, safety laboratory test, ECG or vital signs, etc) is defined as the last assessment of that parameter immediately prior to the start of the first dose of ZS during the Correction Phase. Typically, the baseline refers to the measurements obtained within 1 day (24 hours) of start of correction phase ZS treatment.

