4.1.3 Visit/Time windows

In principle, analyses will be based on **nominal visit basis**, only if scheduled visit is available. In absence of scheduled visit, the unscheduled visits and discontinuation visit will be mapped according to the below windows and utilized for by-visit analysis (Table 2 and Table 3).

If scheduled visit is missing,

- If an unscheduled visit exists for that visit window, it will be used.
- If two or more unscheduled visits are available for the same window, the one closest to nominal target day will be used.

- If two unscheduled observations are equally close to target day, the last observation will be used.

As outlined in the table, S-K measurement taken within 1 day (2 days on QOD regimen) after last dose will be regarded as on-treatment and used in analysis. Unscheduled S-K measurement taken more than 1 day (2 days on QOD regimen) after last dose of ZS could be mapped to EOS (Follow up) visit.

Table 2 Visit window for correction phase

Study Visit	Nominal Day	Target Day	From	To
1	Screening (CP Baseline)		-	-1
2	CP Day 1 (CP Baseline)	1	1	1
3	CP Day 2	2	2	2
4	CP Day 3	3	3	3
5	CP Day 4	4	4	4
EOS	CP Follow Up	10	5	17

Table 3 Visit window for maintenance phase

Study Visit	Nominal Day	Target Day	From	To*
6	MP Day 1 (MP Baseline)	1	1	1
7	MP Day 2	2	2	3
8	MP Day 5	5	4	8
9	MP Day 12	12	9	15
10	MP Day 19	19	16	22
11	MP Day 26	26	23	39
12	MP Day 54	54	40	67
13	MP Day 82	82	68	95
14	MP Day 110	110	96	123
15	MP Day 138	138	124	151
16	MP Day 166	166	152	179
17	MP Day 194	194	180	207
18	MP Day 222	222	208	235
19	MP Day 250	250	236	263
20	MP Day 278	278	264	291

Study Visit	Nominal Day	Target Day	From	To*
21	MP Day 306	306	292	319
22	MP Day 334	334	320	347
23	MP Day 362	362	348	Last dose + 1 day (2 days, on QOD regimen)
EOS	MP Follow Up	last dose + 7 days	last dose +2 days (+3 days, on QOD regimen)	last dose + 14 days

*S-K measurements more than 1 day (2 days, on QOD regimen) after last dose will be regarded off-treatment and will be mapped to the EOS visit.

Note : Any available measurements regardless of scheduled or unscheduled will be taken into account when summarizing the incidence of certain event based on most extreme (lowest or highest) values in safety evaluation (e.g. analysis of incidence of hypokalemia, etc).

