4.2.2 Demographics and baseline characteristics

Demographic and other baseline characteristics, including disease-related characteristics will be summarized, using the SAF-CP as well as SAF-MP.

Demographic and baseline characteristics are listed in [Table 4](#). Disease-related common baseline characteristics are listed in [Table 5](#).

Table 4 Demographics

Characteristics	Summarized as	Categories
Sex	Categorical	Male, Female
Age	Categorical and Continuous	<65, >= 65 years <75, >= 75 years
Body Weight	Categorical and Continuous	< 65, >= 65 kg
BMI	Continuous	
Height	Continuous	
Race	Categorical	Asian, Other

Table 5 Disease-related characteristics

Characteristics	Summarized as	Categories
CP Baseline S-K	Categorical and Continuous	< 5.5 mEq/L, 5.5-< 6.0 mEq/L, >= 6.0 mEq/L
Baseline eGFR*	Categorical and Continuous:	<15 mL/min/1.73m2, 15-<30 mL/min/1.73m2 30-<60 mL/min/1.73m2 >= 60 mL/min/1.73m2
Comorbidity – Heart Failure	Categorical	Yes, No
Comorbidity - Diabetes	Categorical	Yes, No
Comorbidity - CKD	Categorical	Yes, No

Characteristics	Summarized as	Categories
RAAS Inhibitor Use	Categorical	Yes, No
Diuretic Use	Categorical	Yes, No
On peritoneal dialysis	Categorical	Yes, No

*eGFR derived by Japan guideline formula;

$$eGFR[\text{mL}/\text{min}/1.73\text{m}^2] = \text{SCr}[\text{mg}/\text{dL}]^{-1.094} \times \text{Age}[\text{years}]^{-0.287} (\times 0.739 \text{ for female})$$

All summaries of continuous characteristics will be based on non-missing observations. For categorical characteristics, percentages will be calculated out of the total number of subjects in the analysis set (ie, each denominator includes the number of subjects with missing/unknown values for the characteristic).

Comorbidities will be based on medical history (ongoing), using the following search criteria:

- HF will be searched by standardised MedDRA query (SMQ) (narrow) “Cardiac failure”.
- DM will be searched by SMQ (narrow) “Hyperglycaemia/new onset diabetes mellitus”.
- CKD will be searched by SMQ (narrow) “Chronic kidney disease”.

Current medications were based on concomitant medication used at the time of 1st dose of ZS, using the following search criteria :

- Current RAASi use will be searched by anatomical therapeutic chemical (ATC) class ‘C09’ or ‘C03DA’
- Current Diuretic use will be ATC class ‘C03’, ‘C02LG’, ‘C07CB’, ‘C09BA’, or ‘C09DA’

Medical history

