4.2.7.2 Clinical Laboratory evaluation

Change from baseline over time

For continuous variables, observed values and changes from baseline to each post-baseline visit (including last on-treatment value) will be summarized by descriptive statistics.

For categorical variables, shift table from baseline to post-baseline visit (including last on treatment value) will be summarized by number (%) of subjects with each category.

Laboratory abnormalities

The incidence of hypokalemia will be evaluated by tabulating the proportion of subjects in each study phase with a lowest S-K assessment (regardless of scheduled or unscheduled) <3.5 mmol/L (mild hypokalemia) and will be repeated for a more severe definition of < 3.0 mmol/L (moderate hypokalemia) and of < 2.5 mmol/L (severe hypokalemia).

Other potentially clinically significant laboratory abnormalities will also be identified based on the most extreme (lowest and/or highest) post-baseline values and tabulated with number and proportion of subjects meeting each criterion.

Table 7 Potentially Clinically Significant Abnormalities for Laboratory Values

Variable	Unit	Low	High
Chemistry			
Calcium	mg/dL	< 7.0	> 11.0
Inorganic Phosphorus	mg/dL	< 2.0	> 6.5
Albumin	g/dL	< 2.0	> 6.0
Bicarbonate	mmol/L	< 15	> 35
Glucose	mg/dL	< 60	> 300
Potassium	mmol/L	< 3.0	> 6.0
Sodium	mmol/L	< 120	> 160
Total Protein	g/dL	< 4.0	> 10.0
Magnesium	mg/dL	< 0.9	> 4.0
ALP	IU/L	-	> 3xULN
GGT	IU/L	-	> 3xULN
AST	IU/L	-	> 3xULN
ALT	IU/L	-	> 3xULN
Total Bilirubin	mg/dL	-	> 3xULN
Hematology			
Hematocrit	%	< 28	> 55
Hemoglobin	g/dL	< 8	> 20
Platelet Count	x 10 ⁹ /L	< 50	> 600
WBC	x 10 ⁹ /L	< 2.0	> 14

Additional laboratory data summaries

Shift table for UACR categories

Shift table form subjects with UACR in categories of 0-< 30 mg/g (normoalbuminuria), 30-< 300 mg/g (microalbuminuria) and >= 300 mg/g (macroalbuminuria) will be summarized using baseline and last on-treatment values.

Shift table for eGFR categories

Shift tables for subjects with eGFR in categories of 0-< 15 mL/min/1.73 m², 15-<30 mL/min/1.73 m², 30-< 60 mL/min/1.73 m², >= 60 mL/min/1.73 m² will be summarized using baseline and last on-treatment values.

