4.2.7.3 Vital signs

Summary statistics for changes from baseline over time (including last on treatment) for each parameters (SBP, DBP and body weight) will be provided.

In addition, potentially clinically significant abnormal changes at any time post-baseline will be summarized with number of subjects and proportions.

Table 8 Potentially Clinically Significant Abnormalities for Vital Signs

Parameter	Direction	Criterion
SBP	Low	Value <= 90 mmHg and decreased >= 20 mmHg from baseline
	High	Value >= 180 mmHg and increased >= 20 mmHg from baseline
DBP	Low	Value <= 50 mmHg and decreased >= 15 mmHg from baseline
	High	Value >= 105 mmHg and increased >=15 mmHg from baseline

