4.2.7.4 ECGs

Number of subjects with clinically significant abnormality (as assessed by investigator) will be summarized for baseline and post-baseline visits. Summary for most extreme value and last on treatment evaluation will also be presented.

Summary statistics for changes from baseline over time (including last on treatment value) for each parameter (heart rate (HR), P, PR, QRS, QT and QTcF) will be provided. Here QTcF will be derived by below formula.

$$QTcF = \frac{QT}{(60 / HR)^{1/3}}$$

where, QT is in msec and HR is in bpm.

Abnormal prolongation of QTc (QTcF) will be summarized based on criteria specified in the table below. The most extreme (highest) value for a subject during treatment will be used this summary.

Table 9 **Categorical evaluation of QTc prolongation**

Parameter	Criterion
QTcF	>450 msec
	>480 msec
	>500 msec
Change from baseline in QTcF	>30 msec
	>60 msec

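### Table 7 laboratory abnormality counts take no account of baseline status, so in this single-arm study they can mix pre-existing with new abnormalities

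*SAP*

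**What the plan says.** SAP section 4.2.7.2 first covers hypokalemia. It then says that other laboratory abnormalities are "identified based on the most extreme (lowest and/or highest) post-baseline values and tabulated with number and proportion of subjects meeting each criterion". The limits are in Table 7, "Potentially Clinically Significant Abnormalities for Laboratory Values". Each is a fixed low or high value or, for the liver parameters, a multiple of the upper limit of normal. No criterion has a baseline element.

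The note under Table 3 (section 4.1.3) makes every sample eligible for such summaries: "Any available measurements regardless of scheduled or unscheduled will be taken into account when summarizing the incidence of certain event".

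A baseline is available. For parameters other than S-K, section 4.1.2.1 says it "is defined as the last assessment of that parameter immediately prior to the start of the first dose of ZS during the Correction Phase". For S-K it defines two baselines, one for each phase.

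Other safety domains do refer to baseline:
- Vital signs (Table 8) need both a limit and a change, for example "Value <= 90 mmHg and decreased >= 20 mmHg from baseline".
- For ECGs, Table 9 sets absolute QTcF limits and, separately, limits for "Change from baseline in QTcF". Investigator-assessed abnormality is summarized at baseline as well as afterwards.
- Adverse events (section 4.2.7.1) count as treatment-emergent only if they begin once dosing has started.

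For laboratory data, baseline enters through summaries of change for continuous variables, through shift tables for categorical ones ("For categorical variables, shift table from baseline to post-baseline visit"), and through shift tables for UACR and eGFR.

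**The concern.** A subject who enters beyond a Table 7 limit and stays there is counted in the same way as one who crosses it during treatment. In a controlled trial the comparison arm would carry a similar share of pre-existing abnormality. Here there is no such arm, and laboratory assessments are among the primary safety variables in section 3.1.

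The SAP foresees subjects for whom this could happen. Table 5 has a category for CP baseline S-K of 6.0 or more, while the Table 7 upper limit for potassium is above 6.0. Table 5 also has rows for eGFR below 15 and "On peritoneal dialysis". A reader of the final table could take its percentages as the rate at which abnormalities arose during the study, and the table would offer no means of correcting that.

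**Working it through.** The SAP states no figure on this point, so there is none to reproduce. The check has two parts.

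**1. Does another planned output supply the missing information?**
- Change from baseline for continuous variables (section 4.2.7.2) describes the group. It does not show which flagged subjects were abnormal at entry.
- Shift tables are specified for categorical variables, UACR and eGFR. Every Table 7 parameter is a continuous measurement, and neither UACR nor eGFR is in Table 7. No shift table is therefore specified for the Table 7 limits.
- The potassium analyses in section 4.2.4.1 give change from both baselines, the proportion in each category by visit, and subgroups by baseline S-K. They use cut-offs of 3.5 and 5.0, and do not identify subjects above 6.0 both at entry and afterwards.
- The bicarbonate analysis gives change from baseline and the proportion within the reference range by visit. It is not tied to the Table 7 limits of below 15 and above 35.

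None of these separates new from pre-existing abnormality for a Table 7 criterion.

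**2. How large could the mixing be?**

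Let b be the share meeting a criterion at baseline, p the chance that such a subject meets it again afterwards, and r the risk of a new abnormality in the others. All three are assumptions.

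- Displayed proportion = b × p + (1 − b) × r
- Share of the count already abnormal at baseline = b × p / [b × p + (1 − b) × r]
- New abnormality among those at risk = (1 − b) × r / (1 − b) = r

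With p = 0.8 and r = 5%:

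| b | b × p | (1 − b) × r | Displayed | Share already abnormal | New among at risk |
|---|---|---|---|---|---|
| 0% | 0% | 5.0% | 5.0% | 0% | 5.0% |
| 2% | 1.6% | 4.9% | 6.5% | 25% | 5.0% |
| 5% | 4.0% | 4.75% | 8.8% | 46% | 5.0% |
| 10% | 8.0% | 4.5% | 12.5% | 64% | 5.0% |
| 20% | 16.0% | 4.0% | 20.0% | 80% | 5.0% |

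For scale, take the 150 subjects planned in section 1.3 (the Maintenance Phase safety set may be smaller). At b = 5%, 150 × 0.05 × 0.8 = 6.0 pre-existing cases and 150 × 0.95 × 0.05 = 7.1 new ones would be counted together as 13.1.

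Over b from 0 to 20%, p from 0.5 to 1.0 and r from 2% to 5%, the share already abnormal runs from 0% (b = 0) to 0.20 / (0.20 + 0.80 × 0.02) = 93%.

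**Where the effect is small.** Low-potassium counts are hardly touched: subjects enter with S-K of at least 5.1 and start the Maintenance Phase after an i-STAT value of 3.5 to 5.0. For the same reason, potassium above 6.0 in the Maintenance Phase is generally not uninterrupted carry-over from entry. The carry-over for potassium belongs mainly to the Correction Phase.

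**The case against.** The strongest reply is that this is a reporting convention and not an error. The SAP calls these values potentially significant and post-baseline. It does not call them new or treatment-emergent. All analyses are descriptive (section 4.1.1), and new clinical events are captured as treatment-emergent adverse events. The difference from Table 8 is no contradiction, since Table 9 also uses absolute QTcF limits without a baseline condition, beside its change limits. Potassium and bicarbonate have further baseline-referenced analyses.

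Much of this stands. It lowers the weight of the point but does not remove it, because none of those outputs shows how many of the subjects counted under a Table 7 criterion met it before treatment.

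Three stronger readings are tempting, and the SAP supports none of them:
- A reader might infer that this is a renal population in which many subjects enter beyond the limits. The population is defined by hyperkalemia, CKD is a yes/no comorbidity, and eGFR categories extend to 60 and above. Table 5 lists reporting categories, not expected frequencies. Only potassium has a link within the document between an entry category and a Table 7 limit, and even there a value of exactly 6.0 does not exceed the limit.
- A reader might infer that the SAP presents pre-existing disease as an on-treatment effect. The text says post-baseline, and section 4.2.7.2 sets no on-treatment window for these counts.
- A reader might take the illustrative percentages as the expected distortion. They rest entirely on assumed inputs.

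**Conclusion.** The point holds as a cheap improvement. Table 7 counts are not conditioned on baseline, and no baseline count or shift table accompanies them. Without a control arm they can therefore combine pre-existing and new abnormalities within a primary safety output. The displayed proportion can be read as the new-onset proportion only if essentially nobody meets the criterion at entry.

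The size cannot be determined from the SAP, which gives no baseline prevalence. Under the assumed ranges, the share of counted subjects who were abnormal from the start runs from 0% to 93%. It may be negligible for criteria rarely met at entry and hardly matters for low potassium. No internal contradiction is shown.

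**What to change.** Keep the present count. For each Table 7 criterion, low and high separately, and for each study phase, add:
- the number of subjects meeting the criterion at baseline;
- the number and percentage with a new abnormality, with subjects not meeting the criterion at baseline and having at least one post-baseline value as denominator.

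State the baseline in the text. For parameters other than S-K, use the pre-Correction Phase value already defined in section 4.1.2.1. For S-K, use the CP baseline in Correction Phase tables and the MP baseline in Maintenance Phase tables. A subject who enters above 6.0, is corrected and later rises above 6.0 is then counted as new in the Maintenance Phase. With the CP baseline that subject would drop out of the new count.

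The cost is additional columns in a planned table and a denominator that differs by criterion and has to be displayed. No new data are needed.

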4.2.7.3 Vital signs

Summary statistics for changes from baseline over time (including last on treatment) for each parameters (SBP, DBP and body weight) will be provided.

In addition, potentially clinically significant abnormal changes at any time post-baseline will be summarized with number of subjects and proportions.

Table 8 Potentially Clinically Significant Abnormalities for Vital Signs

Parameter	Direction	Criterion
SBP	Low	Value <= 90 mmHg and decreased >= 20 mmHg from baseline
	High	Value >= 180 mmHg and increased >= 20 mmHg from baseline
DBP	Low	Value <= 50 mmHg and decreased >= 15 mmHg from baseline
	High	Value >= 105 mmHg and increased >=15 mmHg from baseline

4.2.7.4 ECGs

Number of subjects with clinically significant abnormality (as assessed by investigator) will be summarized for baseline and post-baseline visits. Summary for most extreme value and last on treatment evaluation will also be presented.

Summary statistics for changes from baseline over time (including last on treatment value) for each parameter (heart rate (HR), P, PR, QRS, QT and QTcF) will be provided. Here QTcF will be derived by below formula.

$$QTcF = \frac{QT}{(60 / HR)^{1/3}}$$

where, QT is in msec and HR is in bpm.

Abnormal prolongation of QTc (QTcF) will be summarized based on criteria specified in the table below. The most extreme (highest) value for a subject during treatment will be used this summary.

Table 9 **Categorical evaluation of QTc prolongation**

Parameter	Criterion
QTcF	>450 msec
	>480 msec
	>500 msec
Change from baseline in QTcF	>30 msec
	>60 msec

5. INTERIM ANALYSES

An interim analysis is planned in this study for the purpose of regulatory submission. The data cut-off for interim analysis will be when the last subject passed the Visit 17. The interim analysis will include safety/efficacy evaluation for the correction phase as well as safety/efficacy evaluation for maintenance phase up to Visit 17.

6. CHANGES OF ANALYSIS FROM PROTOCOL (NOT APPLICABLE)

7. REFERENCES (NOT APPLICABLE)

8. APPENDIX

8.1 Focus of Interim Analysis

As in section 5, one interim analysis (IA) including data up to Visit 17 is planned.

In principle, all planned analysis for safety and efficacy analyses will be carried out with the subset of data up to Visit 17, hence the target time period should be replaced as such.

In addition, the following variables will be scoped out since the data is expected to be immature at the time of IA.

- S-K analysis - change from last maintenance visit to follow up visit
- Questionnaire related to low dose regimen (5g QOD or 2.5g QD)
- SF36v2

SIGNATURE PAGE

This is a representation of an electronic record that was signed electronically and this page is the manifestation of the electronic signature

Document Name: d9482c00001-sap-ed-4		
Document Title:	Statistical Analysis Plan Edition 4	
Document ID:	[REDACTED]	
Version Label:	4.0 CURRENT LATEST APPROVED	
Server Date (dd-MMM-yyyy HH:mm 'UTC'Z)	Signed by	Meaning of Signature
[REDACTED]	[REDACTED]	Author Approval
[REDACTED]	[REDACTED]	Content Approval

Notes: (1) Document details as stored in ANGEL, an AstraZeneca document management system.
